Is transabdominal sonography comparable to transvaginal sonography for eligibility assessment prior to medical abortion?

[name] MD and [name] MD
[name] MD MSc
[name] MD MPH
Columbia University

April 6, 2016 (Last IRB Approval 02/20/2018)

Contact information:

[name]: [contact], [contact]

[name]: [contact], [contact]

Project summary

Ultrasound use in the assessment of medical abortion eligibility varies by practice site. The National Abortion Federation (NAF), the Society of Family Planning (SFP), and the World Health Organization (WHO) guidelines do not recommend the routine use of ultrasonography; however, many institutions and practices still require this as part of clinic protocol. Furthermore, many clinicians routinely perform transvaginal sonography (TVS), a more invasive assessment than transabdominal ultrasound (TAS). Reliance on ultrasound in general, and TVS specifically, decreases access to medical abortion by requiring facilities to purchase and maintain an ultrasound machine, employ trained staff, and perform high-level disinfection (HLD) between examinations. Studies have investigated ways to improve access to medical abortion through a variety of approaches to simplifying care and removing barriers in a variety of practice settings.

Our project takes a health services research approach to simplifying medical abortion. We will perform a multicenter, randomized controlled trial in practices that routinely use TVS to compare how often clinicians order additional testing prior to medical abortion after the use of either TVS or TAS to assess medical abortion eligibility. We plan to study providers of different clinical backgrounds and in different clinical settings. We anticipate enrolling approximately 800 patients receiving care from about 30 providers over 6-8 months. Clinicians who routinely provide medical abortion with TVS at Columbia University Medical Center (CUMC) and Planned Parenthood of Central and Greater Northern New Jersey (PPCGNNJ) will participate.

Women who present for medical abortion will be eligible for this study, and will undergo a routine evaluation including relevant history, abdominal examination, and randomization to receive either TVS or TAS. Following evaluation, providers will make a clinical decision regarding the patient's eligibility for medical abortion, and will proceed with usual care. We will evaluate the proportion of women in the TVS and TAS groups for whom providers ordered additional testing or additional visits prior to making a decision regarding eligibility.

Our primary study outcome will be the proportion of women whose clinician orders additional evaluation after sonography and prior to determination of medical abortion eligibility. We hypothesize this proportion will be greater among those randomized to TAS (non-inferiority boundary of 80%). That is, if clinicians order additional testing in less than 20% of women undergoing TAS, we will consider TAS to be non-inferior to TVS.

Our second major outcome will be patient satisfaction after ultrasound examination. We hypothesize satisfaction will be greater among those randomized to TAS. Following study activities, each participant will complete a satisfaction questionnaire regarding the type of ultrasound she received (TVS or TAS) using a visual analog scale (VAS) and be asked, if she were to require an ultrasound in the future, which she would prefer.

The results from this study could demonstrate that when TAS is used, clinicians order additional testing in a greater proportion of patients than when TVS is used. However, we hypothesize this difference in proportions will fall within a non-inferiority boundary of 80%. Although we expect a difference, we anticipate that this difference in proportions will not be so large that using TAS instead of TVS will be burdensome to providers, clinics, or patients. Many providers in the US already have TVS capabilities and HLD, and may desire to continue using this tool. For such providers, however, switching from TVS to TAS for most patients could reduce costs and increase patient satisfaction. For potential providers who do not have TVS capabilities, our results will help to estimate how often TAS would be sufficient to provide care versus how often patients might need a referral for additional testing.

1. Description of the project

1.1 Rationale and objectives of the study

1.1.1 Rationale

Medical abortion accounts for an increasing proportion of abortions performed in the United States; as of 2012, 20.8% of all abortions were medical abortions.¹ Medical abortion use, however, lags behind the large increase in access some, including Finer and colleagues, anticipated when mifepristone was first introduced in the United States; most medical abortions are still performed by physicians and at facilities where surgical abortion is also offered.^{2,3,4} Many barriers to access remain, including the routine reliance on ultrasound for pregnancy dating, supported by legislative requirements as well as specific clinic protocols and provider preferences.^{5,6} Routine use of ultrasonography and particularly TVS may be a holdover secondary to its use in early clinical trials of medical abortion efficacy - its use has remained a part of many providers' clinical practice despite evidence that it is not always necessary. Proposals to improve access include simplification of the medical abortion process by eliminating routine sonography, eliminating the initial in-person visit,⁷ home use of mifepristone,^{8,9,10} involving more non-physician clinicians in care,^{11,12,13,14,15} increasing services offered in the primary care setting,^{16,17,18,19} allowing for remote forms of follow-up,^{20,21,22,23,24} and numerous other proposed strategies.^{25,26,27} Many of the approaches under investigation are either directly or indirectly related to telemedicine, which is increasingly being used in clinical settings to increase access to care, both in the rural United States, and around the world, and is acceptable to both patients and providers.^{28,29,30,31,32,33,34,35}

Many U.S. abortion providers will not prescribe mifepristone (Mifeprex) for first trimester medical abortion without confirming early intrauterine pregnancy (IUP) by ultrasound, and these early dating ultrasounds are commonly performed transvaginally. Without ultrasound, providers are concerned about underestimating gestational age or missing a miscarriage or ectopic pregnancy. Although ectopic pregnancy is rare among women seeking abortion,^{36,37,38} serious morbidity could occur due to delayed diagnosis. Organizations including NAF,^{39,40,41} WHO,⁴² the American College of Obstetricians and Gynecologists (ACOG),⁴³ and others^{44,45} recommend ultrasonography at the physician's discretion. The Mifeprex prescribing information also supports ultrasound only as needed,⁴⁶ yet many sites still require this as part of standard clinic protocol.

The routine use of TVS or TAS requires facilities providing medical abortion to purchase and maintain an ultrasound machine and employ trained and certified staff. TVS (but not TAS) additionally requires the use of HLD between examinations.⁴⁷ These factors can be burdensome or even prohibitive in many clinic settings. HLD requirements are particularly cumbersome; HLD requires expensive equipment up front, expensive supplies (including the proprietary disinfection solution) on an on-going basis, and costly replacement of probes which degrade with repeated transfers and disinfection. Furthermore, the time required for disinfection between patients interferes with clinic flow and operations. For example, the Trophon EPR high level disinfection system has a 7.5 minute disinfection cycle. In addition, providers or staff must detach the probe from the US machine, wipe off the ultrasound gel, run the disinfection cycle, wipe off the chemical solution, and replace the probe, a process that can easily take 15 minutes. Less expensive HLD systems take even longer, with some disinfection cycles lasting up to 45 minutes, and also may require clinics to have negative pressure ventilation systems to avoid toxicity from the disinfectant. The Centers for Disease Control and Prevention (CDC) has stringent guidelines on both instrument maintenance and healthcare facility auditing.^{48,49} Hospitals are generally in compliance secondary to Joint Commission requirements; however, few practices and clinics are in compliance given these onerous requirements and related costs.

Studies have examined outcomes of medical abortion provided in settings without routine use of ultrasound (such as many locations outside the United States), discussed below in section 1.2. In the proposed study, we will quantify the proportion of women whose providers order additional testing to determine medical abortion eligibility and will compare this proportion between those who received TVS and those who received TAS. We will assess patient satisfaction with each method of ultrasound and compare these results. Our literature review yielded no prior studies examining outcomes of TVS compared with TAS, nor are there any randomized controlled trials including acceptability as an outcome. We will collect data from a range of providers who currently routinely rely on TVS.

This study, specifically, would be of value for the many clinicians who currently use TVS for all medical abortion patients and could support using TAS rather than TVS in a majority of these patients. The results could also provide guidance on how often practice settings without TVS and HLD would be able to provide medical abortion, and for which patients. Such settings could include primary care or rural clinics, any low volume clinics, or those where the costs and time associated with the HLD required for use of TVS prohibit or limit the provision of medical abortion. In addition, even high-volume specialty family planning clinics would benefit from a reduction in use of TVS. One of our collaborators anticipates the cost of implementing HLD in their clinical setting would be at least \$100,000 in capital costs alone. If TVS is used infrequently, a busy clinic could make do with one HLD system. However, if every patient receives TVS, the costs associated with such frequent HLD use will be much higher. If our results show routine use of TAS only requires a small increase in the proportion of patients who receive additional testing prior to medical abortion, it could be both cost-effective and possibly more satisfactory to women to provide TAS for most patients. Cost savings could come from decreased use of HLD itself, increased lifespan of transvaginal probes, decreased time spent for patients to undress and dress for exams, and overall streamlined patient flow. We therefore propose a randomized controlled trial aimed at improving the health care processes around provision of medical abortion and provider assessment of eligibility.

In the US, many providers have sonography available and use it routinely. However, even in the US, many clinics may seek to offer medical abortion without sonography, and other researchers are studying this type of approach. This proposed study will evaluate a more intermediate change in practice, primarily geared towards the large number of providers who routinely provide transvaginal ultrasound. For those providers, moving from TVS to TAS could be both cost effective and acceptable to patients.

1.1.2 Objectives and hypotheses

We hypothesize that for the majority of patients seeking medical abortion, history plus TAS will be comparable (non-inferior) to history plus TVS in the assessment of medical abortion eligibility. In our own recent clinical experience, approximately 5.1% (standard error 2.0%) of patients required further clinical testing after TVS before determination of eligibility. Conversely, 94.9% of patients did not require additional testing. Our objectives include:

Primary Outcomes:

1. **Hypothesis 1:** We hypothesize that history and TAS will be sufficient to determine eligibility in more than 80% of patients (thus our non-inferiority boundary is 80%).
 - a. Evaluate how often the provider orders additional tests (see table 1, in Appendix) prior to providing medical abortion, but after:
 - i. History plus TAS or,
 - ii. History plus TVS
 - b. Evaluate whether the results for TAS exceed the non-inferiority boundary of 80%

2. Hypothesis 2: We hypothesize that patient satisfaction and acceptability will be greater for TAS compared to TVS, based on visual analog scale rating performed by patients following visit. We found no direct data to inform us about the likely size of the difference in acceptability of TVS compared to TAS, as this has not previously been studied (see Section 1.2).
 - a. Assess which ultrasound modality is preferable (“In the future, if you had the choice to receive either TVS or TAS, which would you prefer?”)
 - b. Evaluate if acceptability varies according to patient characteristics including:
 - i. Gestational age
 - ii. Ultrasound experience
 - iii. Abortion or other obstetric experience
 - iv. Additional factors (e.g. age)

Secondary Outcomes: Identify patient and provider characteristics associated with ordering additional tests:

- a. Gestational age (GA) by LMP (≤ 35 days vs. 35-49 days vs. > 49 days, vs. uncertain GA)
- b. Body mass index (BMI) and history of Cesarean delivery
- c. Provider type or experience (physician, APC)
- d. Site (CUMC, PPCGNNJ)
- e. Secular trends within the study (first third of patients seen by providers vs. last third of patients)
- f. Early pregnancy failure

Note: The use of sonography or other strategies for follow-up and cost-effectiveness analyses are also important, but are beyond the scope of this project.

1.2 Previous related studies

As noted in section 1.1.1, related studies include those comparing various methods of pregnancy dating to one another, as well as those that more specifically consider outcomes of medical abortion when ultrasound is only used “as indicated,” and not routinely. Some of these have examined the overall effectiveness and safety of medical abortion outside of the United States, often in places without access to ultrasound, or where it is not used on a routine basis, revealing few complications or adverse events.^{50,51,52,53,54} Multiple studies have evaluated the use of any ultrasound prior to medical abortion,^{55,56,57,58,59,60,61} including two review articles suggesting that in most cases clinicians can use LMP to estimate gestational age and routine sonography is unnecessary.^{62,63}

None of these studies compared TVS and TAS for determining gestational age or eligibility, need for further testing, or patient acceptability. In 2011, Kulier and Kapp⁶⁴ performed a review to determine whether the use of pre-abortion ultrasound had an effect on safety or efficacy, but found no published data addressing this question.

Despite the evidence provided by previous studies, the largest medical abortion provider in the US, Planned Parenthood Federation of America (PPFA), routinely uses TVS for most patients seeking medical abortion. CDC recommendations for HLD of all endoprobes, however, make continued routine TVS use unsustainable. Given the great scrutiny PPFA receives, the organization will only change its guidelines in this regard with high quality evidence supporting an alternative and reliable method of pregnancy dating.

While many providers continue to routinely use ultrasound, TAS may be a less costly, more widely available, and acceptable alternative to TVS. Lohr et al⁶⁵ compared TAS to TVS prior to medical abortion

and found that abdominal sonography was 100% sensitive for detecting a gestational sac but only 68% sensitive for detecting an embryonic pole; the sensitivity decreased further as BMI increased. This study did not address practice implications of switching to TAS. We have found no prior studies looking at whether women who receive TAS prior to medical abortion then undergo more additional testing compared to TVS. This question is particularly important because of the dramatic new expenses related to implementing HLD requirements.

Research on the acceptability of ultrasound modalities for patients is also limited. One study from 1997 considered acceptability of TVS in the first trimester, finding that it was overall acceptable and well-tolerated.⁶⁶ Others have assessed the acceptability of TVS for diagnostic purposes (such as assessing follicular development and ruling out pelvic pathology).⁶⁷ One small study evaluated acceptability of TVS in 107 women presenting with vaginal bleeding in the first trimester, finding that 99% would agree to have a TVS if needed in the future.⁶⁸ While women in these studies found TVS acceptable, no randomized trials evaluate acceptability of these ultrasound modalities in women presenting for abortion. We were unable to find prior studies using a VAS to quantify patient satisfaction for a diagnostic test such as ultrasound, as most similar studies use a Likert scale or other measurement tools.

1.3 Design and methodology

1.3.1 Research design and general methodological approach

This will be a randomized controlled trial comparing TAS to TVS in medical abortion eligibility assessment. With this trial, we aim to improve healthcare processes under real-world conditions at specific clinics where providers now routinely use TVS prior to medical abortion. We will consult the SPIRIT (Standard Protocol Items: Recommendations for Interventional Trials) 2013 guidelines^{69,70} and the CONSORT guidelines, specifically the Practihc (Pragmatic Randomized Controlled Trials in Health Care) reporting guidelines.^{71,72,73} Study protocols will closely match usual care at these sites to help ensure high generalizability of the results of this pragmatic trial.

To evaluate clinician practices at different sites, we plan to enroll women at a hospital-based clinic system (including sites serving Medicaid patients and a faculty practice serving commercially insured patients), and one Planned Parenthood affiliate. Sites will vary in location, ranging from urban clinics to large suburban practices. This will provide diverse study participants and providers. Please see Table 2 (in appendix) for further details on each potential site. Currently, these sites routinely perform TVS before medical abortion.

1.3.1.a: Sites

We will enroll participants at Columbia University Medical Center (CUMC) and Planned Parenthood of Central and Greater Northern New Jersey affiliate (PPCGNNJ). We met with [name], Vice President of Research Development at PPCGNNJ, to discuss our proposed study at length and visited these clinics. Clinics affiliated with CUMC and PPCGNNJ have relevant research experience, including randomized controlled trials and abortion research.

1.3.1.b: Participants

Study participants will include women with an estimated gestational age up to 70 days based on LMP, who desire medical abortion and present to any of our study sites for care. Study participants will complete a questionnaire regarding demographic information as well as experiences with abortion, including medical abortion specifically, delivery, miscarriage, TAS, and TVS. Further inclusion and

exclusion criteria are listed below in section 1.3.2. Study forms will not include any personal identifiers and all participants will be assigned study identification numbers to protect confidentiality.

1.3.1.c: Training, Study Coordinators

A study coordinator at each site will be on location during patient care sessions when medical abortion is provided. The study coordinator will obtain informed consent from all patients at time of enrollment. Study coordinators will also be responsible for ensuring completion of all study documents including: baseline patient and provider characteristics; information on history, physical exam, and imaging results via chart abstraction; and subsequent clinical outcomes for any individual who did not receive medical abortion on the date of study enrollment. As clinic charting and routine practice vary between sites (for example, PPCGNNJ uses paper charts while CUMC uses an electronic medical record system), study coordinators will receive standardized training on all study protocols and additional practice in chart abstraction based on study site.

Prior to study initiation, the investigators will practice chart abstraction for up to 100 charts from each clinical site to 1) improve abstraction tools and familiarize study staff with differing medical record systems, 2) ascertain a more precise estimate of the proportion of patients who need further testing, and 3) troubleshoot any potential problems. The investigators will then train the coordinators in chart abstraction prior to study initiation. Investigators will provide coordinators with 10 charts where further testing was ordered and 20 charts where no additional testing was ordered, to develop skills in relevant chart abstraction.

1.3.1.d: Training, Providers

Prior to participation, providers who routinely offer medical abortion at the study sites will complete a questionnaire regarding professional characteristics. Investigators will provide a training session for all providers at each site to review TAS (i.e. techniques and standardized reporting) as we assume some providers have less experience with this when compared to TVS in early pregnancy. This training session will help minimize differences in TVS and TAS related to provider experience or variability in current practice. In addition, prior to participant enrollment, each clinic site will have a one-week “run-in period,” during which providers will perform both TVS and TAS to accustom providers and clinic staff to study protocols. Study coordinators will abstract charts using study forms during this run-in period for all study endpoints.

1.3.1.e: Intervention

Using the appointment log, the attending physician will identify women scheduled for abortion services that match eligibility criteria and provide these names to the onsite study coordinator. The attending physician can delegate identifying eligible study participants to the onsite coordinator, depending on clinic flow and protocols. Coordinators will explain the study, enroll patients, obtain informed consent, and administer a baseline questionnaire.

All patients seeking medical abortion will undergo routine intake, history, and exam per regular clinic protocol. The study will not require additional testing outside of routine care, which can include a detailed menstrual and reproductive history, measurement of height and weight, or performance of a urine pregnancy test. Prior to ultrasound, study coordinators will provide the sonographer with a sealed, opaque, and sequentially numbered envelope indicating ultrasound assignment (TVS or TAS), and the appropriate test will be performed (see section 1.3.3 for additional details on randomization). After completion of the assigned ultrasound, the provider will use all available information to make a clinical

decision, and the woman will either proceed to receive a medical abortion or undergo further testing if required by the provider. We expect that some participants who do not require additional testing may decide to undergo surgical abortion, due to personal preference or due to gestation age and they will not be excluded from analysis.

Coordinators will abstract information from patient records regarding clinical characteristics (BMI), ultrasound results (including if a miscarriage was diagnosed), plan of care, and whether any further testing was ordered or performed (including type of testing). Coordinators will abstract this information within one week of the index visit. All study sites include this documentation in the clinical record.

1.3.1.f: Outcomes

After history and the assigned ultrasound examination, providers will make an assessment and clinical plan for that participant. That plan of care may include provision of medical abortion that day or additional testing (see Table 1). For example, if a provider is concerned about ectopic pregnancy, further testing could include a pelvic exam, transfer to the emergency department, or additional tests or interventions. Study coordinators will abstract the details of additional evaluation performed from patient charts.

While we will enroll only patients specifically presenting for medical abortion, we will collect data for women who are found to be at too advanced a gestational age to proceed with medical abortion, those who decide during the course of their evaluation that they would prefer an aspiration procedure, those who are diagnosed with miscarriage or ectopic pregnancy, and those who decide to continue the pregnancy.

At the end of their visit, study participants will complete a standardized questionnaire including a 100 mm visual analog scale (VAS) to assess the acceptability of the type of ultrasound they were randomized to receive. We will therefore be able to compare acceptability of ultrasound between women randomized to receive TVS or TAS. We will also ask whether these participants would prefer TVS or TAS in future gynecologic care.

In summary, the main outcomes of this study are: 1) how often the provider orders additional testing in each randomization group (TVS or TAS); and 2) patient acceptability scores for each US modality. Secondary outcomes will include subgroup analyses, including provider type, provider experience, site, and patient characteristics. However, we anticipate some limitations to such analyses based on sample size and will be focusing on the two primary outcomes.⁷⁴

1.3.1.g: Other

We will register our trial with ClinicalTrials.gov. Please see section 1.3.9 for more information regarding data management.

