1.3.10 Data analysis

First, we will evaluate baseline characteristics of all women entered into this study. We will also evaluate if randomization was successful in creating comparable groups. We will use a test of difference in proportions to compare outcomes in this study. We will compare the overall proportions with additional testing. We will also compare acceptability of TVS vs. TAS and assess satisfaction. For our secondary analyses, we will compare subgroups defined by provider and provider type, clinic site, and based on clinical characteristics including GA, BMI, and previous C/S. We will evaluate whether there is a difference in the proportion receiving additional tests in the TVS and TAS groups that is associated with any of these variables (physician provider compared to APC provider, Ob/Gyn physician compared to Family Medicine physician, obese participant compared to normal weight participant, etc.). We will use SAS to analyze our findings, as both fellows currently have access to SAS and use it routinely as part of graduate school studies.

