Our base assumption is that 5-7.5% of patients will need additional testing after TVS. We also expect to see the greatest variability between TVS and TAS findings between 35 and 49 days estimated gestational age, compared to those less than 35 days and greater than 49 days. Prior to 35 days, we expect neither TVS nor TAS to be able to identify a gestational sac for most women (thus resulting in additional testing in both groups), and after 49 days we expect both TVS and TAS to usually be able to identify a gestational sac with fetal pole (thus resulting in less additional testing in both groups). Between 35 and 49 days, however, we expect some proportion of patients to have a gestational sac with or without a yolk sac identifiable on TVS but not on TAS and in this range, the proportion of patients for whom clinicians order additional tests may be higher. We expect the proportion where providers encounter uncertainty, leading to additional testing, would be greater at earlier gestational ages and perhaps in those patients with an uncertain LMP or irregular cycle (questions we will be formally evaluating as described in Hypothesis #1, section 1.1.2).

Further, we expect clinicians to order more testing after TAS because TAS has lower resolution than TVS. The transabdominal probe is further from the uterus, and thus uses a lower frequency to achieve a longer focal length. TAS typically uses a 3-6 mHz probe while TVS uses a probe with 5-10 mHz frequency. TAS may have even less resolution in an obese patient as the distance to the uterus will be greater; obesity's effect of decreasing resolution was noted in a prior study by Lohr et al.⁶³

We expect additional testing after TVS to mainly include serial quantitative beta-hCG tests and additional visits for a repeat sonogram. We expect that additional testing after TAS would include the same, plus same-day use of TVS if TAS inadequate to confirm eligibility for medical abortion. At all study sites, immediate TVS will be available

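### The acceptability VAS, a primary outcome, is rated at the end of the visit, when some TAS women will also have had TVS, and no test suited to a 0–100 mm score is named

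*Combined protocol and SAP*

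**What the plan says.** Section 1.1.2 lists patient satisfaction and acceptability, measured by VAS, as Hypothesis 2 under the primary outcomes. Section 1.3.1.f says the investigators "will be focusing on the two primary outcomes", one of which is the acceptability score for each modality.

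On timing, section 1.3.1.f states: "At the end of their visit, study participants will complete a standardized questionnaire including a 100 mm visual analog scale (VAS". The same sentence gives the purpose as "to assess the acceptability of the type of ultrasound they were randomized to receive". The Project summary describes the questionnaire as "regarding the type of ultrasound she received (TVS or TAS) using a visual analog scale (VAS", and places it after study activities.

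On what happens before the rating, section 1.3.11 expects testing after TVS to be mainly serial hCG and return visits for another sonogram. After TAS it expects the same, "plus same-day use of TVS if TAS inadequate to confirm eligibility for medical abortion", and adds: "At all study sites, immediate TVS will be available". Appendix Table 1 counts TVS after TAS, on the same day or at a later visit, as additional testing.

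On analysis, section 1.3.10 says: "We will use a test of difference in proportions to compare outcomes in this study". It then says that acceptability will be compared, without a method. Section 1.3.11 bases the sample size on additional testing alone. No SD, expected difference, power, alpha or sidedness is given for the VAS.

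**The concern.** Hypothesis 2 is about the scan. Section 1.3.11 expects women to prefer TAS because they can stay dressed and the examination is less intrusive, and it sets that preference against the cost of more testing as a trade-off. The two sides of a trade-off have to be measured separately. A rating given at the end of the visit can carry reaction to a follow-on TVS, or to being told that more tests are needed, into the acceptability score. The first of these is expected in the TAS arm only. The second occurs in both arms, but at rates that the plan expects to differ. The burden of additional testing may then count on both sides.

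The planned look at acceptability by gestational age (section 1.1.2) is exposed too. Section 1.3.11 expects TVS and TAS findings to diverge most between 35 and 49 days, so women scanned both ways would probably cluster there.

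Separately, a test of proportions cannot be applied to a 0–100 mm score as it stands, so this primary outcome has no specified test.

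**Working it through.** **The plan's own figure.** Table 3, row 1 (5% additional testing after TVS, 10% after TAS, margin 10 points, one-sided alpha 5%, power 80%):

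n = [0.95×0.05 + 0.90×0.10] × (1.645 + 0.842)² / (0.10 − 0.05)² = 340.04

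This agrees with the stated 340 per arm. It concerns the other primary outcome. There is no VAS figure to reproduce, so what follows is illustrative.

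**Inputs from the documents.** 340 per arm (Table 3); about 800 enrolled, so 400 per arm (Project summary); additional testing after TAS of 10% (Table 3, row 1) or 20% (the 80% boundary).

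**Assumptions, since the documents give no values.** SD of the VAS 20 to 30 mm; shift in the rating of a woman scanned both ways 10 to 30 mm, in either direction; SD unchanged by the shift; two-sided 5% and 80% power for the VAS.

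**Detectable difference** = (1.960 + 0.842) × SD × √(2/n)

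| SD (mm) | n = 340 per arm | n = 400 per arm |
|---|---|---|
| 20 | 4.3 mm | 4.0 mm |
| 25 | 5.4 mm | 5.0 mm |
| 30 | 6.4 mm | 5.9 mm |

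**Movement of the TAS mean** = share scanned both ways × shift. The share takes all additional testing after TAS as same-day TVS. Because additional testing also includes hCG, return visits and pelvic examination, each share is an upper bound for its scenario.

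| Share of TAS arm | Women, of 340 | 10 mm | 20 mm | 30 mm |
|---|---|---|---|---|
| 10% | 34 | 1 mm | 2 mm | 3 mm |
| 20% | 68 | 2 mm | 4 mm | 6 mm |

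With a 20 mm shift, the movement at the planning rate is 2/6.4 to 2/4.3, or about 31% to 47% of the detectable difference. At the boundary it is 4/6.4 to 4/4.3, or about 62% to 93%.

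**Effect on the test**, at 340 per arm, SD 25 mm and a 20 mm shift, using the same upper-bound shares:

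- True 6 mm advantage for the TAS scan: power is 88% with nobody scanned both ways. If those ratings fall, it is 55% at a 10% share and 18% at 20%. If they rise by contrast with TVS, it is about 99% or more.
- No true difference between the scans: if those ratings rise, the result is significant in favour of TAS 18% of the time at a 10% share and 55% at 20%, against a nominal 2.5% in that direction.

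**News of more testing.** If being told that more tests are needed shifted ratings by the same 20 mm in both arms, it would partly cancel: (0.10 − 0.05) × 20 = 1 mm at the planning rates, and (0.20 − 0.05) × 20 = 3 mm at the boundary.

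**The case against.** The strongest reply is that this is a pragmatic trial meant to match usual care. Rated at the end of the visit and analysed by assignment, the VAS is a sound randomized comparison of starting with TAS and adding TVS when needed. That stands. A reader might infer that the comparison is biased or invalid, and the documents do not support that. They show only that it answers a different question from the modality comparison in Hypothesis 2.

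Section 1.3.1.f already directs the item at the randomized scan, which should reduce carry-over. The Project summary's wording about the scan received differs for a woman who had both, but it is one word in a summary and the questionnaire is not in the documents. It should not be read as proof of a defective item.

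It is also tempting to take 5% to 20% as the share of TAS women who will have same-day TVS. That is not supported: 5% is the planning rate after TVS, and 10% and 20% cover every kind of additional test.

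Nor do the documents say that the VAS will be dichotomised. Loss of information from doing so is hypothetical; what can be said is that no method for the score is named.

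Finally, section 1.3.1.e has coordinators abstract the type of further testing, so women scanned both ways can be identified. This permits description. It cannot recover what they would have said before the second scan.

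An objection to re-timing also has force. An unblinded provider who learned of a stated preference for TAS or TVS before deciding on further testing might be influenced, and that decision is the other primary outcome, which section 1.3.12 concedes is subjective. Women who have had both scans also give the better-informed answer on future preference. Both points argue for moving the VAS alone.

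**Conclusion.** The point holds in a limited form. As planned, the primary VAS comparison can mix reaction to the assigned scan with reaction to follow-on testing, with same-day TVS expected only in the TAS arm. The direction of the effect cannot be predicted. With an assumed 20 mm shift it is at most 2 mm at the plan's 10% rate and 4 mm at its 20% boundary. It comes close to the detectable difference only at the 20% share with the smallest SD. SDs and shifts are assumptions, and the true same-day TVS rate may be well below these shares. The confirmed gap in analysis is that no summary measure, test or sidedness is given for the VAS; the proportions test properly serves additional testing and the binary preference item. This is worth correcting because it affects a primary outcome and is cheap to correct. It does not undermine the trial.

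**What to change.** **Collection.** Have the on-site coordinator, who already hands over the allocation envelope just before the scan, give the VAS alone immediately after the assigned scan and before any further test. The item should name the assigned scan, and the answer should not be shown to the provider. Keep the future-preference question and the general items at the end of the visit.

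**Analysis.** Add to section 1.3.10 that the VAS is analysed as randomised, as a continuous score. Report the difference in means with a two-sided 95% confidence interval from a linear model adjusted for site (the stratification factor, section 1.3.3) and previous TVS and TAS experience (on the participant questionnaire, section 1.3.1.b). Use a Wilcoxon test as a sensitivity analysis. Keep the test of proportions for the preference item. Use the abstracted type of further testing to describe the women scanned both ways.

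**Cost.** One short form handed over earlier and a few lines of analysis plan, with no extra visit or staff. The downsides are a brief pause between the assigned scan and the consultation or same-day TVS, at sites where section 1.6 already expects some strain on workflow, and a VAS that reflects the scan and no longer the whole visit.
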